8. TRIAL PROCEDURES

8.1 Trial procedures

The Trial Flow Chart - Section 7.0 summarizes the trial procedures to be performed at each visit. Individual trial procedures are described in detail below. It may be necessary to perform these procedures at unscheduled time points if deemed clinically necessary by the investigator.

8.1.1 Administrative Procedures

8.1.1.1 Informed Consent

The Investigator must obtain documented consent from each potential subject prior to participating in a clinical trial.

General Informed Consent

Consent must be documented by the subject's dated signature or by the subject's legally acceptable representative's dated signature on a consent form along with the dated signature of the person conducting the consent discussion.

A copy of the signed and dated consent form should be given to the subject before participation in the trial.

The initial informed consent form, any subsequent revised written informed consent form and any written information provided to the subject must receive the IRB/ERC's approval/favorable opinion in advance of use. The subject or his/her legally acceptable representative should be informed in a timely manner if new information becomes available that may be relevant to the subject's willingness to continue participation in the trial. The communication of this information will be provided and documented via a revised consent

form or addendum to the original consent form that captures the subject's dated signature or by the subject's legally acceptable representative's dated signature.

The informed consent will adhere to IRB/ERC requirements, applicable laws and regulations and Sponsor requirements.

8.1.1.2 Inclusion/Exclusion Criteria

All inclusion and exclusion criteria will be reviewed by the investigator or qualified designee to ensure that the subject qualifies for the trial.

8.1.1.3 Medical History

A medical history will be obtained by the investigator or qualified designee. Medical history will include all active conditions, and any condition diagnosed within the prior 10 years that are

considered to be clinically significant by the Investigator. Details regarding the disease for which the subject has enrolled in this study will be recorded separately and not listed as medical history.

8.1.1.4 Prior and Concomitant Medications Review

Prior Medications

The investigator or qualified designee will review prior medication use, including any protocol-specified washout requirement, and record prior medication taken by the subject within 28 days before starting the trial. Treatment for the disease for which the subject has enrolled in this study will be recorded separately and not listed as a prior medication.

Concomitant Medications

The investigator or qualified designee will record medication, if any, taken by the subject during the trial. All medications related to reportable SAEs and ECIs should be recorded as defined in Section 8.2.

8.1.1.5 Disease Details and Treatments

Disease Details

The investigator or qualified designee will obtain prior and current details regarding disease status.

Prior Treatment Details

The investigator or qualified designee will review all prior cancer treatments including systemic treatments, radiation and surgeries.

Subsequent Anti-Cancer Therapy Status

The investigator or qualified designee will review all new anti-neoplastic therapy initiated after the last dose of trial treatment. If a subject initiates a new anti-cancer therapy within 30 days after the last dose of trial treatment, the 30 day Safety Follow-up visit must occur before the first dose of the new therapy. Once new anti-cancer therapy has been initiated the subject will move into survival follow-up.

8.1.1.6 Trial Compliance (Medication/Diet/Activity/Other)

Compliance with Metformin will be determined using drug diary and pill counts performed on day 1 of each cycle. Patients who take less than 80% of their prescribed dose of nivolumab and/or metformin in the first 2 cycles due to reasons other than toxicity, clinical or radiographic disease progression will be considered inevaluable for the primary endpoint and will be replaced.

8.1.2 Clinical Procedures/Assessments

8.1.2.1 Adverse Event (AE) Monitoring

The investigator or qualified designee will assess each subject to evaluate for potential new or worsening AEs as specified in the Trial Flow Chart and more frequently if clinically indicated. Adverse experiences will be graded and recorded throughout the study and during the follow-up period according to NCI CTCAE Version 4.0 (see Section 11.2). Toxicities will be characterized in terms regarding seriousness, causality, toxicity grading, and action taken with regard to trial treatment.

For subjects receiving treatment with nivolumab all AEs of unknown etiology associated with nivolumab exposure should be evaluated to determine if it is possibly an event of clinical interest (ECI) of a potentially immunologic etiology (termed immune-related adverse events, or irAEs, see section 6.2.2).

Please refer to section 8.2 for detailed information regarding the assessment and recording of AEs.

Winship Cancer Institute's Clinical Trials Office will perform the quality assurance and quality control checks on this clinical trial. Before enrollment of any subject in this study, CTO personnel and the Investigator will review the protocol; the Investigator's Brochure; the CRFs/electronic CRFs and instructions for completion; the informed consent process; and the procedure for reporting AEs and SAEs.

8.1.2.2 Full Physical Exam

The investigator or qualified designee will perform a complete physical exam during the screening period. Clinically significant abnormal findings should be recorded as medical history. A full physical exam should be performed during screening,

8.1.2.3 Directed Physical Exam

For cycles that do not require a full physical exam per the Trial Flow Chart, the investigator or qualified designee will perform a directed physical exam as clinically indicated prior to trial treatment administration.

8.1.2.4 Vital Signs

The investigator or qualified designee will take vital signs at screening, prior to the administration of each dose of trial treatment and at treatment discontinuation as specified in the Trial Flow Chart (Section 6.0). Vital signs should include temperature, pulse, respiratory rate, weight and blood pressure. Height will be measured at screening only.

8.1.2.5 Eastern Cooperative Oncology Group (ECOG) Performance Scale

The investigator or qualified designee will assess ECOG status (see Section 11.1) at screening (within 14 days of day 1 cycle 1), prior to the administration of each dose of trial treatment and discontinuation of trial treatment as specified in the Trial Flow Chart.

8.1.3 Tumor Imaging and Assessment of Disease

Response Evaluation Criteria in Solid Tumors (RECIST) 1.1 Criteria for Evaluating Response in Solid Tumors

RECIST version 1.1* will be used in this study for assessment of tumor response. While either CT or MRI may be utilized, as per RECIST 1.1, CT is the preferred imaging technique in this study.

8.1.3.1 Tumor Tissue Collection and Correlative Studies Blood Sampling

Paired biopsies (biopsy#1) will be obtained at baseline from all 28 patients within 28 days before Cycle 1 day 1 after consent is signed, subject #1-9, 19-23 (14 patients in total) will get post treatment biopsy (biopsy#2) cycle 1 Day 1 (same day or up to 5 days later) and subject# 10-18, 24-28 (14 patients in total) will get post treatment biopsy (biopsy#2) C1 Day 15 (same day or up to 5 days later). Most accessible metastatic disease tumor site will be biopsied by Emory Interventional Radiology. Same site will be biopsied at biopsy#1 and biopsy#2. We don't believe biopsy site bias the study as any metastatic site which is deemed safe and accessible can be biopsied. 3 core biopsies will be obtained each time. If a patient undergoes biopsy#1 and refuse biopsy#2 this subject will be replaced. The obtained tissues will be handled in the following way:

- 1) RNAlater for RNA stabilization and tissue storage
- 2) Formalin-fixed paraffin block with one cut H&E stained slide
- 3) Liquid nitrogen frozen tissue in cryo-preservation vials

All collected tissues are stabilized and stored in -80°C freezers (RNAlater stabilized, OCT embedded, short term storage) or the vapor phase of a liquid nitrogen freezer (long term storage) in single use aliquots. All FFPE tissue blocks are stored in a climate-controlled storage room that is temperature (less than 27°C) and humidity controlled.

Tissue will be evaluated using IHC or immunofluorescence to measure relevant immune markers (i.e. CD3, CD4, CD8, CD163, PD-1, PD-2, PDL-1, MIF, TAM and stromal/ vascular markers). When sufficient quantities of fresh tissue is available, it will also be dissociated and flow cytometry will be used to determine the phenotypic characteristics of cell populations in the tumor microenvironment. Tissue will be preserved for future exploratory studies including genomic profiling.

Peripheral blood samples

Approximately 20 mL of peripheral blood will be collected prior to initiation of study therapy (at baseline), cycle 1 day 1, cycle 1 day 15, Cycle 3 Day 1 and at progression. The peripheral blood mononuclear cells will be isolated from these samples and stored in -80°C freezers until analysis. Samples will be evaluated for:

- i. Determine whether there are phenotypic changes in of T-cell or myeloid cell surface markers (including co-stimulatory/immune checkpoint molecules) in PBMCs after treatment. Samples will be collected at baseline, cycle 1 day 1, cycle 1 day 15, Cycle 3 Day 1 and at progression.
- ii. Determine whether functional changes are evident in PBMCs in response to treatment and whether these data correlate with clinical outcome measures. Samples will be collected at baseline and week 10th. Pending quantity of cells a variety of assays may be performed, including but not limited to intracellular cytokine production and expression of CD107.

Shipping and handling instructions

After appropriate processing, the blood samples, tissue blocks, slides or frozen tissue samples will be sent to:

[name] Laboratory
[name]
[name]
Winship Cancer Institute of Emory University
[name]

On the day that the specimens are to be shipped, notify [name] at [contact], and [name] at [contact] of the pending specimen shipments. Include the Fed-Ex tracking number in the email.

Research blood contact Information:

[name]. [contact]
[name]., MPH [contact]

Methods and materials per Lab Manual**Table 5 Laboratory Tests**

| Hematology | Chemistry | Urinalysis | Other |
|------------------------------|----------------------------------|---|--|
| Hematocrit | Albumin | Blood | Serum β -human chorionic gonadotropin† |
| Hemoglobin | Alkaline phosphatase | Glucose | (β -hCG)† |
| Platelet count | Alanine aminotransferase (ALT) | Protein | PT (INR) |
| WBC (total and differential) | Aspartate aminotransferase (AST) | Specific gravity | aPTT |
| Red Blood Cell Count | Lactate dehydrogenase (LDH) | Microscopic exam (If abnormal) | Total triiodothyronine (T3) |
| Absolute Neutrophil Count | Carbon Dioxide ‡ | results are noted | Free tyroxine (T4) |
| Absolute Lymphocyte Count | (CO_2 or bicarbonate) | Urine pregnancy test † | Thyroid stimulating hormone (TSH) |
| | Calcium | | |
| | Chloride | | Blood for correlative studies |
| | Glucose | | |
| | Phosphorus | | |
| | Potassium | | |
| | Sodium | | |
| | Magnesium | | |
| | Total Bilirubin | | |

| Hematology | Chemistry | Urinalysis | Other |
|------------|--|------------|-------|
| | Direct Bilirubin (If total bilirubin is elevated above the upper limit of normal) | | |
| | Total protein | | |
| | Blood Urea Nitrogen | | |

† Perform on women of childbearing potential only. If urine pregnancy results cannot be confirmed as negative, a serum pregnancy test will be required.

‡ If considered standard of care in your region.

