1. STUDY SYNOPSIS

| |
|---|
| 
Title of Study: Phase II trial of Nivolumab and Metformin in patients with treatment refractory MSS metastatic Colorectal Cancer
 |
| 
Study Centers: Emory University Winship Cancer Institute
 |
| 
Study Phase: Phase II
 |
| 
Objectives:
 
Primary Objective:
 
▪ The primary endpoint of this study is to Evaluate the effect of metformin in combination with nivolumab on the overall response rate (ORR) (Primary Objective) as assessed by RECIST.1.1 
Secondary Objectives:
 
▪ To determine the effect of the metformin and nivolumab combination on clinical (PFS, OS) outcomes and biochemical (CEA) response.▪ To compare the effect metformin and nivolumab combination on immune and metabolic biomarkers in the tumor microenvironment and systemic circulation (pre and post treatment paired biopsies required). |
| 
Trial Design/Methodology: Single arm phase II study. 28 patients with previously treated (previously treated with fluoropyrimidine, oxaliplatin, irinotecan and EGFR inhibitor – if RAS wildtype) metastatic CRC will be started on metformin and nivolumab combination.
 
Treatment
 
1. Patients will start taking metformin 500 mg po BID for 3 days, then 500 mg am and 1000 mg pm for 4 days, then 1000 mg po bid for 1 week. Patients of the study will get paired biopsies as outlined in study calendar.2. If a patient cannot tolerate metformin 1000 mg po BID the patient will resume the metformin dose which was tolerable3. After 2 weeks of metformin only therapy (lead-in period) patients will start nivolumab 480 mg IV q4 weeks and continue metformin 1000 mg PO BID (or the tolerated dose of Metformin).4. Restaging scans will be performed at the end of cycle 2, then every 8 weeks for 2 years.5. Correlative assays will include- immune profiling of TILs and circulating lymphocytes, plasma cytokine levels and metabolic biomarkers. These will be performed at baseline at baseline, cycle 1 day 1, cycle 1 day 15, Cycle 3 Day 1 and at progression 
Treatment regimen and trial diagram:
 |

Main criteria for exclusion:

- MSI status
- Autoimmune conditions that may require systemic steroids or other immunosuppressive treatments
- Pregnancy or breast feeding

Investigational product and administration:

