8.1.5.4 Cycle 1 Day -7 phone call

- Metformin
- Review of adverse events, dosing compliance and concomitant medication (by clinical trial coordinator via phone call)

8.1.5.5 Cycle 1 Day 1

- Record concomitant medications
- Vitals (temperature, HR, BP and RR)
- History and physical exam, pill diary and pill count, blood glucose log for diabetic patients
- ECOG performance status
- Toxicity assessment
- Laboratory Assessments
 - Hematology hemoglobin, hematocrit, red blood cell count, white blood cell count with differential and platelet count
 - Chemistry sodium, potassium, chloride, bicarbonate, magnesium, calcium, phosphorus, blood urea nitrogen, creatinine, glucose (random), total bilirubin, LDH, total protein, ALP, ALT, AST, and albumin
- Blood sample 20 cc for correlative work
- **Subject# 1-9, 19-23** (14 patients in total) will get biopsy#2 of paired biopsy (same day or up to 5 days later)
- Continue metformin
- Nivolumab will be started after biopsy#2 (same day or up to 5 days later).
- Nivolumab 480 mg will be administered as a 30-minute IV infusion in the infusion center. Given the variability of infusion pumps, a window of -5 minutes and +10 minutes is permitted (i.e., infusion time is 30 minutes: -5 min/+10 min).

8.1.5.6 Cycle 1 Day 15

- Record concomitant medications
- Vitals (temperature, HR, BP and RR)
- History and physical exam, pill diary and pill count, blood glucose log for diabetic patients
- ECOG performance status

- Toxicity assessment
- Laboratory Assessments
 - Hematology hemoglobin, hematocrit, red blood cell count, white blood cell count with differential and platelet count
 - Chemistry sodium, potassium, chloride, bicarbonate, magnesium, calcium, phosphorus, blood urea nitrogen, creatinine, glucose (random), total bilirubin, LDH, total protein, ALP, ALT, AST, and albumin
 - Tumor marker – CEA
- Blood sample 20 cc for correlative work
- The second half of the patients **Subject #10-18, 24-28** (14 patients in total) will get biopsy#2 of paired biopsy (same day or up to 5 days later)
- Continue metformin

8.1.5.7 Cycle 2 Day 1

- Record concomitant medications
- Vitals (temperature, HR, BP and RR)
- History and physical exam, pill diary and pill count
- ECOG performance status
- Toxicity assessment
- Laboratory Assessments
 - Hematology hemoglobin, hematocrit, red blood cell count, white blood cell count with differential and platelet count

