9.1.4 Clinical Supplies Disclosure

This trial is open-label; therefore, the subject, the trial site personnel, the Sponsor-investigator and/or designee are not blinded to treatment. Drug identity (name, strength) is included in the label text; random code/disclosure envelopes or lists are not provided.

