For the biomarker study, descriptive statistics will be first used to summarize biomarker endpoints, including analyses of tumor biopsies. Biomarker data will also be displayed graphically, where appropriate. Depending on whether data is normally distributed, t-test or Wilcoxon rank sum test will be used to compare each biomarker between any two groups stratified by response or other factors, respectively. General linear model (GLM) will be used to compare each biomarker between responders and nonresponders with and without adjusting for other factors. Logistics regression model will be further employed to test the adjusted effect of biomarker on the response rate after adjusting for other factors.

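### Second-biopsy timing is set by enrolment number in open runs, so any tissue comparison of metformin alone with the combination is partly confounded with enrolment order

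*Combined protocol and SAP*

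**What the plan says.** Section 8.1.3.1 takes a baseline biopsy from every patient and then splits the second biopsy by subject number: "subject #1-9, 19-23 (14 patients in total) will get post treatment biopsy (biopsy#2) cycle 1 Day 1", while "subject# 10-18, 24-28 (14 patients in total) will get post treatment biopsy (biopsy#2) C1 Day 15". Footnote h of the Section 7 calendar and visit sections 8.1.5.5 and 8.1.5.6 give the same lists.

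On treatment at those times, the synopsis says: "After 2 weeks of metformin only therapy (lead-in period) patients will start nivolumab 480 mg IV q4 weeks". Section 8.1.5.5 (Cycle 1 Day 1) adds: "Nivolumab will be started after biopsy#2 (same day or up to 5 days later".

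On the choice of tissue: "Most accessible metastatic disease tumor site will be biopsied by Emory Interventional Radiology". The same site is used for both biopsies of a patient. On replacement: "If a patient undergoes biopsy#1 and refuse biopsy#2 this subject will be replaced". The plan does not say which timing the replacement receives.

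The trial is open-label; Section 9.1.4 says of the drug supplies that "random code/disclosure envelopes or lists are not provided". The documents describe no randomisation or concealment of biopsy timing. For biomarkers, Section 10.2 offers tests to "compare each biomarker between any two groups stratified by response or other factors". It names neither biopsy timing nor enrolment order as a factor, and describes its analyses as hypothesis generating.

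**The concern.** Tissue on metformin alone and tissue on the combination always come from different patients. In each Simon stage, every patient biopsied at Day 1 enrols before every patient biopsied at Day 15. Anything that changes over accrual and affects the biomarker change therefore falls unequally on the two groups: the kind of patient enrolled, the metastatic site that happens to be accessible, or the behaviour of an assay. Such a change could be read as an effect of adding nivolumab. All 28 timings are also printed in the protocol, so whoever enrols the next patient knows which biopsy that patient will have.

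At stake is the interpretation of research biopsies taken for a secondary objective, in a trial whose main hypothesis is that metformin alters the tumour microenvironment.

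**Working it through.** **Inputs.** The subject numbers are from 8.1.3.1. The stage sizes (18, then 10 more to reach 28) are from 10.1. The documents give no accrual dates, so enrolment position stands in for calendar time with equal spacing. The synopsis, the calendar and 8.1.5.5 place the first nivolumab dose at Cycle 1 Day 1, and the calculation uses that. Table 1 in 6.1.1 lists only metformin for Cycle 1, and calendar footnote c ties nivolumab to the second biopsy without limiting this to the Day 1 group. Those passages need reconciling.

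**1. The plan's own figure.** Day 1 group: 9 + 5 = 14. Day 15 group: 9 + 5 = 14. Together they cover 1 to 28 once each, so the 14/14 split reproduces. It is 9:9 in stage 1 and 5:5 in stage 2.

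**2. Imbalance in enrolment position.**
- Day 1 group: (45 + 105)/14 = 10.71.
- Day 15 group: (126 + 130)/14 = 18.29.
- Gap: 106/14 = 7.57 positions; 7.57/27 = 0.28 of the span.
- Stage 1 only: means 5 and 14; 9/17 = 0.53 of that shorter span.
- Correlation of timing with position: 0.47 overall, 0.87 within each stage.

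A stage-1 stop is not remote. With no response in 18 as the stopping outcome, its probability is 0.95^18 = 0.40 at a true response rate of 5%, and 0.85^18 = 0.05 at 15%.

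**3. Bias if the within-patient change drifts.** Suppose the change drifts linearly by D SD over 28 patients. Bias = D × 7.57/27.

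| Assumed drift D | Bias in the contrast | Rejection rate of a nominal two-sided 5% test, no true effect |
|---|---|---|
| 0.5 SD | 0.14 SD | 6% |
| 1 SD | 0.28 SD | 11% |
| 2 SD | 0.56 SD | 30% |

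The rejection rates come from the noncentral t with 14 per group and residual SD 1. At a stage-1 stop with the same drift per patient, the bias is D × 9/27 = 0.33 D. It is 0.53 D only if the whole drift D occurs within those 18 patients.

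**4. Drift in level, after pairing.** A slow additive drift common to both samples of a patient mostly cancels in the change. What remains comes from the roughly two-week longer pair interval in the Day 15 group. For a 1 SD level drift over an assumed accrual of 12, 24 or 48 months, this is 2/52 = 0.04, 2/104 = 0.02 or 2/208 = 0.01 SD, and enrolment order does not affect it.

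**5. Sensitivity of the contrast.** At 80% power and two-sided 5% (assumed), 14 against 14 detects about 1.11 SD, and 9 against 9 about 1.41 SD.

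**6. What randomising achieves.** Permuted blocks within stage (4, 4, 4, 4, 2, then 4, 4, 2) keep 9:9 and 5:5. Over 40,000 simulated lists the position gap averages 0 with SD 0.46; 95% are within 0.86 and the largest is 1.86. Strict alternation leaves a gap of 1 position (1/27 = 0.04 of the span) and stays predictable.

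**7. What adjustment costs.** Adding enrolment order alone gives a variance inflation of 1.28. Adding order and stage gives 3.42, which leaves the information of about 28/3.42 = 8 patients.

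**The case against.** The strongest reply is that this comparison is not a planned analysis. The stated objective is the effect of the combination on paired tissue, and 10.2 refers only to groups defined by response or other factors. No passage says why timing is split. That the split serves to separate metformin from the combination is a reasonable inference, but only an inference. This stands, and it limits the weight of the point.

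Second, each patient's own same-site baseline removes most slow drift in level (step 4). A reader might infer that a 1 SD drift in assay level would produce a 0.28 SD false difference. That holds for unpaired post-treatment levels, not for within-patient change. Frozen and paraffin-embedded tissue can also be assayed in one batch; flow cytometry on fresh tissue is the exception. Pairing does not remove drift in the change itself, such as a shift in case mix that alters response. Section 8.1.3.1 states a belief that biopsy site does not bias the study, but gives nothing on whether the mix of sites is stable over accrual.

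Third, the order is early, late, early, late, so each stage is balanced in number and the confounding is partial.

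Fourth, a reader might infer that staff would steer patients to one timing. The documents show the opportunity but no motive: this is a single centre, and every patient has the same drugs and two biopsies. Nor do they show that the allocation fails when someone is replaced. Inheriting the slot would fit the stated 14 per group; the rule is simply not written down.

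Fifth, blood is sampled at both Day 1 and Day 15 in the same patients, so the blood comparison does not have this problem.

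**Conclusion.** The point holds as an avoidable weakness in an exploratory comparison. The imbalance in enrolment order is a fact of the plan: 7.57 positions, or 28% of the span, and 53% of the shorter span at a stage-1 stop. The resulting bias is conditional. It is about 0.14 to 0.56 SD if the within-patient change drifts linearly by 0.5 to 2 SD over equally spaced accrual, and near zero if only the level drifts slowly. The documents give no drift figure, so this is a range and not a prediction.

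A reader might conclude that the tissue results will show a false nivolumab effect, or that the trial's conclusions are at risk. Neither follows. A false effect could arise but is not shown, and response rate, progression-free survival and overall survival do not depend on biopsy timing.

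Randomising also has a limit. The Day 15 group has had about four weeks of metformin against about two in the Day 1 group, so the contrast would still mix the addition of nivolumab with longer metformin exposure.

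**What to change.** - Assign the timing of biopsy #2 1:1 by permuted-block randomisation within each Simon stage (9:9, then 5:5), and reveal it only after consent and biopsy #1.
- State that a replacement patient takes the timing slot of the patient replaced.
- In 10.2, name the exploratory comparison as within-patient change by timing group. Say that it compares about 2 weeks of metformin alone with about 4 weeks of metformin plus nivolumab, and so does not isolate nivolumab.
- If enrolment is advanced, randomise only the remaining slots and add enrolment order as a covariate in a sensitivity analysis.

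The cost is a short list and a protocol amendment, with no extra patients, biopsies or visits. The enrolment status is not stated. If stage 1 is complete, its confounding cannot be undone: randomising only stage 2 leaves an expected gap of (126 − 45)/14 = 5.79 positions, or 5.79/27 = 21% of the span instead of 28%. The report should then state the enrolment order of the two groups alongside the comparison.
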